8.0 TOXICITIES/SIDE EFFECTS

The recommended daily dietary intake of choline is 500mg per day and the maximum safe level of choline is 3.5 g/day. The amount of ¹¹C-CH to be administered will be at tracer micrograms levels, which are orders of magnitude below the safety limits for choline. Therefore chemical toxicity is not expected. No toxicities associated with "tracer doses" of ¹¹C-CH have been reported. The dose-limiting toxicity is therefore associated solely with the radiation emissions emanating from the ¹¹C radiolabel. The activities of ¹¹C-CH that shall be administered will be up to 10-20 mCi (approximately 6-20mCi). The expected radiation doses from this maximum administration level of 20 mCi is given in total dose column of the table below, which also includes the 0.9 cGy contribution from the low-dose CT (Table 3). Exposure falls within the constraints imposed by an RDRC protocol.

While toxicities are not anticipated on this trial, all patients will have a follow up toxicity assessment by a member of the research team (MD, NP, or RN), either in person or over the phone, 1-3 days following the research scans. The participants will be asked whether they have suffered any adverse events and these will be documented.

Table 3. Radiation Dosimetry Estimates

¹¹C-Choline and Head CT Dosimetry

Target Organ	rad/mCi	¹¹ C-Choline				Total Dose rad	
		Imaging:		Pre-surgical:			
		rad / 10.0	mCi	rad / 2.0	mCi		
Adrenals	0.0630	0.630		0.126		0 0.819	
Brain	0.0290	0.290		0.0580		0.9 1.28	
Breasts	0.0310	0.310		0.0620		0 0.403	
Small Intestine	0.0480	0.480		0.096		0 0.624	
Large Intestine	0.0480	0.480		0.096		0 0.624	
Stomach Wall	0.0480	0.480		0.096		0 0.624	
Kidneys	0.289	2.89		0.578		0 3.76	
Liver	0.207	2.07		0.414		0 2.69	
Lungs	0.0410	0.410		0.0820		0 0.533	
Muscle/Other Tissue	0.0370	0.370		0.0740		0 0.481	
Pancreas	0.0590	0.590		0.118		0 0.767	
Red Marrow	0.0370	0.370		0.0740		0.9 1.38	
Bone surface	0.0560	0.560		0.112		0.9 1.63	
Skin	0.0290	0.290		0.0580		0 0.377	
Spleen	0.111	1.11		0.22		0 1.44	
Gonads	0.0340	0.340		0.0680		0 0.442	
Thymus	0.0370	0.370		0.0740		0 0.481	
Thyroid	0.0350	0.350		0.0700		0.9 1.36	
Urinary Bladder Wall	0.107	1.07		0.214		0 1.39	

1

For bone surfaces, red marrow, and thyroid, the low-dose CT absorbed doses are conservatively estimated as if they were completely in the CT

field of view. All other organs were assigned a CT dose of 0, since they would receive only a negligibly small scatter dose.

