The ^{11}C -CH will be used in this trial, strictly in concordance with the requirements of the Radioactive Drug Research Committee (RDRC). The RDRC permits the study of up to 30 human subjects with a research radiotracer prior to an IND application provided: (1) the radiotracer is not a first in man study, (2) the agent is administered at doses below that which will produce a pharmacologic effect and (3) the projected radiation dose falls within defined limits; namely <3cGy for eyes, bone marrow and testes per injection and <5 cGy per annum; for all other organs <5cGy per injection or <15 cGy per annum. This trial will investigate the distribution of a research agent. The trial is intended to discover where the agent distributes within the head (RDRC justification), as well as address objectives 1 and 2. The individual patient results from this study will not be used for disease diagnosis or to assess treatment response or to change treatment decisions.

Study Scheme:

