Radiographic changes will be defined as progression rather than pseudoprogression within that 24 week window per modified RANO criteria. However, unlike the RANO criteria, the protocol will allow for a broader window of 24 weeks after completion of radiation instead of 12 weeks to maximize enrollment. Progression can only be defined using diagnostic imaging less than 24 weeks after completion of radiation if there is new enhancement outside the radiation field (beyond the high-dose region or 80% isodose line) or if there is unequivocal evidence of viable tumor or histopathologic sampling (ie, >70% tumor cell nuclei in areas, high or progressive increase in MIB-proliferation index compared with prior tissue, or evidence for histologic progression or increased anaplasia in tumor). Given the difficulty of differentiating true progression from pseudoprogression, clinical decline alone, in the absence of radiographic or histologic confirmation of progression, will not be sufficient for definition of progressive disease in the first 24 weeks after completion of radiation. Follow-up brain MRI with and without contrast per standard of care will be used in the assessment of the evolution of these lesions. Further increase in enhancement in subsequent MRI warranting a change in therapy per the treating physician will define progression unless proven otherwise by a histopatholgically confirmed diagnosis. Lesions that stabilize or reduce in size will be deemed consistent with pseudoprogression.

Radiation Exposure (dosimetry). Radiation exposure from ¹¹C-CH PET imaging study has been estimated and published.[55, 56] The critical organ exposures are: kidney 0.64, bladder wall 0.36, and liver 0.26 cGy/mCi with all other organs receiving less than 0.25 cGy per mCi injected. Doses to the most radiation sensitive tissues red marrow, testes and ovaries are 0.075, 0.057, and 0.067 cGy/mCi respectively. The RDRC requires that the administered activity result in <30mSv to the

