radiosensitive tissues that include the lens of the eye, gonads, bone marrow, and GI tract, and <50mSv for all other organs per administration. Dosimetry data for lens of the eye was not available (visual uptake of F-choline was not observed for this organ). Additionally, if more than one administration of the radiotracer will be given, then the study must ensure <50mSv for the radiosensitive organs and <150mSv for all other organs within a single year. These factors taken together influenced the selection of a total administered activity of not more than 14mCi for this study in order to be within compliance with the RDRC dosimetry regulations. The organ dose estimates from this study are provided in Table 3.

Radiosynthesis and Specific Activity of ¹¹C- CH. The ¹¹C-CH drug product will be manufactured in compliance with the current Good Manufacturing Practices (cGMP) requirements at the MSKCC Radiochemistry and Molecular Imaging Probes Core Facility, using the ORA Neptis automated synthesizer. The synthesizer cassettes, and reagents and materials will be supplied by ABX Advanced Biochemical Compounds (Radeberg, Germany). ¹¹C-choline injection contains 30 mCi to 400 mCi in approximately 10 ml of ¹¹C-choline at EOS (End of Synthesis) calibration time in aqueous 0.9% sodium chloride solution. The patient unit dose will consist of 10-20 mCi of ¹¹C-choline. With a molecular weight of 104, 20 mCi of ¹¹C-choline corresponds to 104 mg/mmol x 2x10-6 mmol = 200x10-6 mg = 2x10-4 mg of administered. All manufactured ¹⁸F-FCH drug product batches will be Quality Control (QC) tested to ensure conformance with the acceptance specifications for pH, appearance, radiochemical purity, radiochemical identity, radionuclidic identity, endotoxin levels, sterilizing filter integrity, and residual solvent levels prior to release for patient administration. Sterility testing will be performed post release.

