¹¹C-CH Delivery to the MITS Radiopharmacy from Radiochemistry (RMIP) Core. ¹¹C-CH dose will be delivered by Radiochemistry (RMIP) Core to MITS Clinical Radio-pharmacy in Nuclear Medicine. MITS Clinical Nuclear Pharmacist receives the delivery from RMIP Core and ensures that the study drug is handled, inventoried, stored properly, labeled and dispensed as per AU MITS Physician prescription order. The ¹¹C-CH dose will be drawn and measured in a Dose Calibrator by a MITS Nuclear Pharmacist prior to dispensing. Then, the syringe will be placed in a shielded Carrier and handed over to AU MD or designee for administration. After the dose administration the AU MD returns the Syringe for Residual Measurement by MITS Nuclear Pharmacist. All MITS Radiopharmacy activity will be documented by MITS Nuclear Pharmacist.

PET imaging Protocol. Patients will undergo PET scanning following intravenous administration of up to 10-20 mCi (6-20mCi to permit for decay) of ¹¹C-CH under the regulation and approval of the MSKCC RDRC. 10-20 mCi of ¹¹C-choline will be administered intravenously as a bolus, followed by 10-30 mL of normal saline flush, with the patient already placed on the bed of the scanner unit. Imaging will begin approximately 5 minutes after injection of ¹¹C-choline. We will accrue 6 evaluable research subjects with the purpose of determining the biodistribution within the evolving lesion. No information gleaned from the PET images or biodistribution data shall be used to affect patient management.

Patients will be set up for a static single field of view (15 cm) head scan by means of a scout and low-dose CT scan. ¹¹C-CH will be administered as an intravenous slow bolus with simultaneous initiation of the scan sequence. The patient will be positioned in the PET/CT in the scan ready position prior to the radiopharmacy dispensing the ¹¹C-CH activity. In this way the activity administered to the patient is within 10% of the prescribed activity as required by research PET studies. ¹¹C-CH, for intravenous bolus injection, is a PET imaging agent with a half-life of 20.4 min. Prior studies have shown that tracer uptake plateaus within 15-20 minutes post-injection. A single PET scan will be performed for up to a maximum of 40 min to ensure capture of the uptake.

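### The Table 3 dose totals are presented as doses at 20 mCi but are doses at 13 mCi; at 20 mCi the table's own kidney figure gives 5.78 cGy against a limit of 5 cGy.

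*Combined protocol and SAP*

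**What the plan says.** Section 8.0 gives the activity to be administered as up to 20 mCi and introduces Table 3 as follows: "The expected radiation doses from this maximum administration level of 20 mCi is given in total dose column of the table below". It adds that the totals include 0.9 cGy from the low-dose CT, and ends: "Exposure falls within the constraints imposed by an RDRC protocol".

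The limits are in Section 1.0. Eyes, marrow and testes must stay below 3 cGy per injection, and "for all other organs <5cGy per injection or <15 cGy per annum". Section 7.2 restates the per-administration limits as 30 mSv and 50 mSv. The kidney falls in the other-organs group in both places.

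The maximum activity is stated in two ways:

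- The dosimetry text in Section 7.2 says that the RDRC limits "influenced the selection of a total administered activity of not more than 14mCi for this study".
- The radiosynthesis paragraph of Section 7.2 sets a patient unit dose of 10 to 20 mCi. The PET imaging paragraph says "Patients will undergo PET scanning following intravenous administration of up to 10-20 mCi (6-20mCi to permit for decay"). Section 8.0 repeats 20 mCi as the maximum.

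The dose per mCi is also stated in two ways. Table 3 lists the kidney at 0.289, bladder wall at 0.107 and liver at 0.207 rad/mCi. The dosimetry text in Section 7.2 says: "The critical organ exposures are: kidney 0.64, bladder wall 0.36, and liver 0.26 cGy/mCi".

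**The concern.** Table 3 is the protocol's only worked demonstration that organ doses stay within the RDRC limits, and the study runs under the RDRC without an IND (Sections 1.0 and 14.3). Section 8.0 names radiation as the only dose-limiting toxicity, and Section 14.1 relies on the same dosimetry when it calls the exposure very minimal.

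The printed kidney row shows the problem at once: 0.289 rad/mCi times 20 mCi is not 3.76. If the totals belong to a lower activity, the table does not support the claim made for it. Staff following the imaging paragraph could then give an activity whose kidney dose exceeds the limit while the table appears to show compliance.

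**Working it through.** **Inputs.** From Table 3: dose per mCi, CT dose (0.9 for brain, red marrow, bone surface and thyroid; 0 elsewhere) and total dose for each organ. From Section 1.0: limits of 5 cGy (other organs) and 3 cGy (eyes, marrow, testes) per injection. From Section 7.2: the 14 mCi ceiling and the second set of coefficients. 1 rad = 1 cGy. I take 1 cGy as 10 mSv, as the protocol does when it pairs 5 cGy with 50 mSv.

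**Step 1: which activity reproduces the printed totals?**

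Implied activity = (total − CT) / (dose per mCi). Dose at activity A = (dose per mCi) × A + CT.

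| Organ | per mCi | CT | Printed total | Implied mCi | at 12 mCi | at 13 mCi | at 14 mCi | at 20 mCi |
|---|---|---|---|---|---|---|---|---|
| Kidneys | 0.289 | 0 | 3.76 | 13.01 | 3.47 | 3.757 | 4.05 | **5.78** |
| Liver | 0.207 | 0 | 2.69 | 13.00 | 2.48 | 2.691 | 2.90 | 4.14 |
| Spleen | 0.111 | 0 | 1.44 | 12.97 | 1.33 | 1.443 | 1.55 | 2.22 |
| Bladder wall | 0.107 | 0 | 1.39 | 12.99 | 1.28 | 1.391 | 1.50 | 2.14 |
| Bone surface | 0.056 | 0.9 | 1.63 | 13.04 | 1.57 | 1.628 | 1.68 | 2.02 |
| Red marrow | 0.037 | 0.9 | 1.38 | 12.97 | 1.34 | 1.381 | 1.42 | 1.64 |
| Thyroid | 0.035 | 0.9 | 1.36 | 13.14 | 1.32 | 1.355 | 1.39 | 1.60 |
| Gonads | 0.034 | 0 | 0.442 | 13.00 | 0.408 | 0.442 | 0.476 | 0.680 |

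Across all 19 rows the implied activity lies between 12.97 and 13.14 mCi, and 13 mCi reproduces every total to rounding. Neither 20 mCi, nor the 14 mCi ceiling, nor the 12 mCi from adding the table's 10 and 2 mCi columns does so.

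**Step 2: doses at the stated maximum of 20 mCi, on Table 3 coefficients.**

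- Kidney: 0.289 × 20 = 5.78 cGy. Against 5 cGy this is 5.78 / 5 = 1.16, or 16% over.
- The table's totals understate the tracer dose at 20 mCi by 1 − 13/20 = 35%.
- Activity at which the kidney reaches the limit: 5 / 0.289 = 17.3 mCi.
- The kidney is the only listed organ over its limit. Liver is next at 4.14 cGy against 5. Red marrow (1.64) and gonads (0.68) are below 3.

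**Step 3: the same check on the Section 7.2 coefficients.**

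| Organ | Section 7.2 per mCi | Ratio to Table 3 | at 10 mCi | at 14 mCi | at 20 mCi |
|---|---|---|---|---|---|
| Kidney | 0.64 | 2.2 | 6.4 | 8.96 | 12.8 |
| Bladder wall | 0.36 | 3.4 | 3.6 | 5.04 | 7.2 |
| Liver | 0.26 | 1.3 | 2.6 | 3.64 | 5.2 |

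On these figures the kidney reaches 5 cGy at 5 / 0.64 = 7.8 mCi, so no activity from 10 to 20 mCi would comply, and the 14 mCi ceiling would not either. The text presents them as 11C-choline doses, but the two papers it cites (references 55 and 56) are titled as 18F-fluorocholine and 18F-choline studies.

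**The case against.** The strongest reply is that the protocol contains a compliant ceiling. Section 7.2 says the activity was held to 14 mCi because of the RDRC limits, and at 14 mCi the Table 3 kidney dose is 4.05 cGy. The excess arises only above 17.3 mCi, the upper part of the permitted range, and the RDRC approval is not in the documents, so no actual overdose is shown. That stands: the breach is conditional on the activity given. It does not remove the problem, because the unit-dose paragraph, the imaging instruction and Section 8.0 all allow 20 mCi, and Section 8.0 ties its compliance claim to that figure.

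A second reply is that the larger Section 7.2 doses are probably carried over from the 18F tracer. The titles of the cited papers point that way, as does a remark on lens uptake in the same text that refers to F-choline. This is fair. Step 3 should be read as evidence of an inconsistency that needs clearing up, not as the exposure patients would receive. The papers were not available to settle it.

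Third, the table layout came through text extraction damaged, and a lost column of about 1 mCi could explain 13 rather than 12. That is possible, so the mismatch with the two activity columns carries little weight. It cannot explain 13 rather than 20.

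Finally, this is radiation-safety text and does not touch the SUV endpoints or their analysis. That is true, and it does not make the safety statement correct.

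**Conclusion.** The concern holds and should be fixed before the protocol is relied on for dosing. Two conclusions need only Table 3 and the stated limit. The totals are 13 mCi doses labelled as 20 mCi doses. At 20 mCi the kidney dose is 5.78 cGy, 16% above a limit the protocol says it meets. The contradiction between 14 and 20 mCi, and between the two sets of per-mCi figures, is plain on the face of the text.

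The size of the breach assumes that the Table 3 coefficients are the right ones for 11C-choline. If the Section 7.2 figures were right instead, every activity from 10 to 20 mCi would exceed the kidney limit. The finding concerns regulatory compliance and the accuracy of the safety statement; it is not a prediction of clinical injury.

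**What to change.** 1. State one maximum administered activity and use it in the dosimetry text, unit-dose paragraph and imaging paragraph of Section 7.2 and in Section 8.0. On Table 3 figures it must be below 17.3 mCi for the kidney; 14 mCi would comply. The choice belongs to the sponsor and the RDRC.
2. Confirm one set of 11C-choline coefficients with a source for that tracer, and use it in both Section 7.2 and Table 3.
3. Recompute every Table 3 total at the chosen maximum and label the column with that activity.
4. Remove the 2 mCi pre-surgical column if no such injection is given; Section 7.2 describes a single scan.
5. Keep the compliance sentence in Section 8.0 only if every recomputed organ dose is below its limit.

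The cost is a protocol and RDRC amendment and a recomputed table, with no extra patients or procedures. A lower ceiling also narrows the dosing window for a tracer with a 20.4-minute half-life, which is a modest operational constraint. The stated organ doses become less favourable if the chosen maximum is above 13 mCi.

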9.0 PRIMARY OUTCOMES

We will assess ^{11}C -CH tracer biodistribution within high-grade glioma lesions with MRI findings concerning for pseudoprogression vs. true tumor progression after treatment with radiation. PET imaging metrics will be collected; peak SUV values in the lesion and the tumor to background ratio will be compared to clinical follow-up outcomes based on MRIs.

We expect that there will be low uptake of ^{11}C -CH in perilesional normal brain tissue and SUV measures will correlate with clinical follow-up outcomes, thus supporting more definitive investigation of ^{11}C -CH PET to noninvasively distinguish recurrent tumor (true tumor progression) from necrosis and inflammation (pseudoprogression) in post-treatment MRI-evolving brain lesions.

10.1 CRITERIA FOR REMOVAL FROM STUDY

- Inability to undergo PET/CT scan.
- Found to be ineligible for the protocol as described in the section on Criteria for Patient/Subject Eligibility.
- Patient and/or legal representative requests to withdraw from study for any reason
- Referring physician requests to have patient withdrawn from study for any reason, including believing that it would be in the patient's best interest.

11.0 BIOSTATISTICS

This trial is a pilot study to determine the distribution of ^{11}C -CH using PET imaging in progressive high-grade glioma lesions suspected to represent true tumor progression vs pseudo-progression, following treatment with a course of radiation. The purpose of this trial is to correlate SUV measures from ^{11}C -CH PET with evolving changes on brain MRI in high-grade glioma after radiotherapy. In a small subgroup of patients required surgery, tissue will be analyzed for histopathologic correlate. The data gathered will not be considered definitive, but rather will be used to as preliminary data in support of a larger, definitive study.

The biodistribution of ^{11}C -CH will be measured using PET as a basis for dosimetry. This will be performed with region of interest analysis. The first objective is to determine the organ/tissue uptake and tumor localization following intravenous injection of ^{11}C -CH in patients with high-grade glioma with radiographic progression concerning for progression versus pseudoprogression following treatment with radiation with or without chemotherapy. The group for this analysis comprises 6 high-grade glioma patients who appear to have progression vs pseudoprogression on standard MRI with contrast. Standardized uptake values (SUV) in the brain will be measured and summarized for each patient to describe the organ and tissue uptake of the tracer. The mean SUV along with SUVmax value will be estimated in normal and tumor tissue, and lesion-to-normal brain ratio (LNR) values will be obtained. All patients will then be followed with surveillance brain MRI per standard treatment over a period of 11 months for evolving changes that will confirm the diagnosis of progression versus pseudoprogression as defined in the protocol.

It is anticipated that 1 patient every 2 months will be accrued to this study and the study will be completed in approximately 12 months.

12.1 RESEARCH PARTICIPANT REGISTRATION AND RANDOMIZATION PROCEDURES

12.2 Research Participant Registration

Confirm eligibility as defined in the section entitled Criteria for Patient/Subject Eligibility.

Obtain informed consent, by following procedures defined in section entitled Informed Consent Procedures.

During the registration process, registering individuals will be required to complete a protocol specific Eligibility Checklist. The individual signing the Eligibility Checklist is confirming whether or not the participant is eligible to enroll in the study.

Study staff are responsible for ensuring that all institutional requirements necessary to enroll a participant to the study have been completed. See related Clinical Research Policy and Procedure #401 (Protocol Participant Registration).

12.3 Randomization

No randomization will occur in this study.

13.1 DATA MANAGEMENT ISSUES

A Research Study Assistant (RSA) will be assigned to the study. The responsibilities of the RSA include project compliance, data collection, abstraction and entry, data reporting, regulatory monitoring, problem resolution and prioritization, and coordinating the activities of the protocol study team.

The data collected for this study will be entered into a secure database. Source documentation will be available to support the computerized patient record.

13.2 Quality Assurance

Weekly registration reports will be generated to monitor patient accruals and completeness of registration data. Routine data quality reports will be generated to assess missing data and inconsistencies. Accrual rates and extent and accuracy of evaluations and follow-up will be monitored periodically throughout the study period and potential problems will be brought to the attention of the study team for discussion and action.

Random-sample data quality and protocol compliance audits will be conducted by the study team, at a minimum of two times per year, more frequently if indicated.

13.3 Data and Safety Monitoring

The Data and Safety Monitoring (DSM) Plans at Memorial Sloan-Kettering Cancer Center were approved by the National Cancer Institute in September 2001. The plans address the new policies set forth by the NCI in the document entitled "Policy of the National Cancer Institute for Data and Safety Monitoring of Clinical Trials," which can be found at:

<http://www.cancer.gov/clinicaltrials/conducting/dsm -guidelines /page1>.

The DSM Plans at MSKCC were established and are monitored by the Office of Clinical Research. The MSKCC Data and Safety Monitoring Plans can be found on the MSKCC Intranet at:

<http://inside2/clinresearch/Documents/MSKCC%20Data%20and%20Safety%20Monitoring%20Plans.pdf>

There are several different mechanisms by which clinical trials are monitored for data, safety, and quality. There are institutional processes in place for quality assurance (e.g., protocol monitoring, compliance and data verification audits, therapeutic response, and staff education on clinical research quality assurance) and departmental procedures for quality control, plus there are two institutional committees that are responsible for monitoring the activities of our clinical trials programs: the *Data and Safety Monitoring Committee (DSMC)* for Phase I and II clinical trials, and the *Data and Safety Monitoring Board (DSMB)* for Phase III clinical trials, report to the Center's Research Council and IRB.

During the protocol development and review process, each protocol will be assessed for its level of risk and degree of monitoring required. Every type of protocol (e.g., NIH sponsored, in-house sponsored, industrial sponsored, NCI cooperative group, etc.) will be addressed and the monitoring procedures will be established at the time of protocol activation.

